subscore of the Constant-Murley score remained significantly improved. They were unable to associate the grade of OA to pain relief following IACSI.

This study differs dramatically from clinical practice, where IACSI is normally administered as a single injection. Repeat injections are often delayed, with some surgeons recommending a three month break between injections. Presently, there is an evidence gap with respect to evidence of the effectiveness of single-injection IACSI on clinical and patient-reported outcomes in patients with glenohumeral OA.

5. Specific Aims

To address this deficit in the literature, there are two specific aims:

1. Assess the effectiveness of IACSI in patients with primary osteoarthritis in the shoulder. This will be determined through three patient-reported outcomes measures:
 - ASES (American Shoulder & Elbow Surgeon) score improvement > 20.9 points⁸
 - VAS (Visual Analog Scale) pain score improvement > 1.4 points
 - SST (Simple Shoulder Test) score improvement > 2.4 points
2. Assess clinical and radiographic predictors of success (outlined below) in patients who elect to receive IACSI as treatment for primary osteoarthritis in the shoulder.
 - Clinical
 - Duration of Symptoms
 - Location of pain (Anatomic Diagram, Figure 1)
 - Pain diagrams will be analyzed using a computer overlay protocol and analyzed in a binary matter according to region. Image software (NIH, Bethesda, MD) will be used. Proportions of the patients responding to injection in each anatomic region and groups of regions will be calculated. 95% confidence intervals will be determined.¹
 - History of prior injection
 - Range of motion (Forward elevation in the scapular plane, ER at 0° abduction, IR at 0° abduction)
 - Standardized pain and function scores (VAS pain, SST, ASES)
 - Prior analgesia (OTC, Narcotic)
 - Initial response to anesthetic component (VAS 5-10 min post-injection)
 - Radiographic
 - Joint space narrowing (measured)
 - Subluxation
 - Walch classification
 - Subchondral cysts
 - Samilson & Prieto Radiological Classification
 - Mild Arthrosis: inferior humeral and/or glenoid exostosis < 3mm in height

- Moderate Arthrosis: inferior humeral and/or glenoid exostosis measuring 3mm to 7mm slight gleno-humeral irregularity
- Severe Arthrosis: inferior humeral and/or glenoid exostosis measuring > 7mm gleno-humeral joint narrowing and sclerosis

6. Research Plan

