- Memory loss or inability to complete study measures
- History of allergy to injection medications
- Diabetic patients with patient-reported fasting blood glucose >200
- Prior injection in the ipsilateral shoulder within three months

Data Collection: The following data points and information will be collected for later analysis:

- Patient name
- MRN
- Gender
- Date of birth
- E-mail address
- Telephone number
- Location of pain (pre-procedural pain chart)
- Duration of symptoms
- History of prior IACSI in ipsilateral shoulder
- Prior analgesia
- Shoulder Range of Motion (Forward elevation, External rotation, Internal rotation)
- Radiographic findings
- Date of IACSI
- Date of each follow-up survey
- Results of each standardized pain and function survey

Confidentiality: Once all enrolled subject data is collected, subject PHI will be removed and the data will be maintained by using assigned research identification numbers that uniquely identify each individual. Date of birth will be converted to age, and dates will also be converted to time frames. Coded data will be stored on a secure online database such as REDCap and an Excel spreadsheet on a password protected computer within the Department of Orthopaedics and Rehabilitation. Data will be converted to a SPSS file for analysis which will also be stored on a secure department server. Data will be used only in aggregate and no identifying characteristics of individuals will be published or presented. Only the study team members will have access to these files. After the study is completed, local data will be stored with other completed research studies in a secured storage room until the appropriate time when the research files may be purged according to university policy.

Data Analysis:

Each patient-reported outcome measure will be assessed at each time point pre- and post-injection and grouped according to the grade of shoulder osteoarthritis. Groups will be compared using a one-way ANOVA analysis. Groups with a response to injection (VAS score improvements greater than the minimal clinically important difference) will be compared to those without a significant response. Single multi-level regression analysis will be performed to assess for clinical and radiographic risk factors outlined in Aim Two that may predict corticosteroid injection failure.

7. Possible Discomforts and Risks

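### The OA-grade ANOVAs appear to compare score levels at each visit, so after injection they cannot separate where a grade started from how it responded

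*Combined protocol and SAP*

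**What the plan says.** Section 6, Data Analysis, sets out three analyses.

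- **Grade comparison.** "Each patient-reported outcome measure will be assessed at each time point pre- and post-injection and grouped according to the grade of shoulder osteoarthritis". Then: "Groups will be compared using a one-way ANOVA analysis". The dependent variable is not stated, and no change score, baseline covariate, pairing or grade-by-time term is named. The grading scale is not named either. Section 5, Aim 2, lists the "Samilson & Prieto Radiological Classification" with three levels, and also the Walch classification.
- **Responder comparison.** Response is defined on VAS alone: "Groups with a response to injection (VAS score improvements greater than the minimal clinically important difference".
- **Regression.** It examines "clinical and radiographic risk factors outlined in Aim Two that may predict corticosteroid injection failure". The Aim 2 list includes the Samilson & Prieto grade and the standardized VAS, SST and ASES scores. Failure is not defined.

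Section 5, Aim 1, defines effectiveness as improvement on all three scores, including "ASES (American Shoulder & Elbow Surgeon) score improvement > 20.9 points" and "SST (Simple Shoulder Test) score improvement > 2.4 points". Section 4 says of the one prior study of these injections: "They were unable to associate the grade of OA to pain relief following IACSI".

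**The concern.** One rule covers the pre- and post-injection visits. No change exists at the pre-injection visit, so the rule reads most naturally as a comparison of score levels. The responder comparison in the same paragraph speaks of improvements, which suggests that the authors name change when they mean it.

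Patients are not randomised to an OA grade, so nothing in the design makes the grades start at the same score. An ANOVA on levels at, say, three months asks whether grades differ at that visit. It does not ask whether they responded differently. It can show a grade difference when every grade improved equally, and it can hide a real difference in improvement when the grade that gains most started lowest. Section 4 presents the link between grade and relief as unresolved, so readers are likely to take these ANOVAs as evidence on it.

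**Working it through.** **Inputs from the protocol.** 500 patients (section 6, Subjects); three grades, if Samilson & Prieto is meant (section 5); baseline and five follow-up surveys (section 6). The plan gives no SD, alpha, baseline gap, grade split, retention or correlation, so it has no figure to reproduce.

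**Assumed inputs.** Alpha 0.05; an ASES-like score with SD 20 (also 15 and 25); equal grades, 500/3 ≈ 166 each, or 166 × 0.70 ≈ 116 after 30% loss; baseline/follow-up correlation 0.3 to 0.7.

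**Step 1: what a follow-up difference contains.** For grade g, follow-up mean = baseline mean b(g) + mean change d(g). The difference between grades g and h is therefore [b(g) − b(h)] + [d(g) − d(h)]. With equal change the second bracket is zero, and the follow-up difference is simply the baseline difference.

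**Step 2: level ANOVA under equal improvement.** The noncentrality is λ = n × Σ(m(g) − mean)² / SD². For baseline means spaced 0/2.5/5, Σ = 6.25 + 0 + 6.25 = 12.5, so λ = 166 × 12.5 / 400 = 5.19. With 2 and 495 degrees of freedom the critical F is 3.01, and the rejection probability is 52%. SD 15 gives 78% and SD 25 gives 35% (61% and 25% with 116 per grade).

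**Step 3: allow for the pre-injection ANOVA.** A starting gap misleads most when the follow-up test is significant and the pre-injection test is not. That joint chance is the rejection rate times the simulated share of significant follow-up tests whose pre-injection test is not significant. For 0/2.5/5 with 166 per grade, it is 0.517 × 0.256 = 0.132 at correlation 0.7 and 0.517 × 0.396 = 0.205 at correlation 0.3.

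| Baseline gap | n per grade | Level ANOVA rejects | Share with pre-injection test not significant (correlation 0.7 to 0.3) | Joint chance |
|---|---|---|---|---|
| 0/1.5/3 | 166 | 21.2% | 0.449–0.678 | about 9–14% |
| 0/2.5/5 | 166 | 51.7% | 0.256–0.396 | about 13–21% |
| 0/4/8 | 166 | 91.2% | 0.054–0.077 | about 5–7% |
| 0/1.5/3 | 116 | 15.9% | 0.500–0.733 | about 8–12% |
| 0/2.5/5 | 116 | 37.8% | 0.333–0.516 | about 13–19% |
| 0/4/8 | 116 | 78.0% | 0.121–0.184 | about 9–14% |

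**Step 4: ANOVA on change, same scenarios.** Mean change is equal across grades, so the test should hold its nominal level. Simulation (6,000 runs, correlations 0.3 to 0.7) gave 4.6–5.7%.

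**Step 5: masking.** Let the worst grade improve 5 points more than the best, with the middle grade halfway.

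- If the worst grade starts 5 points lower, the follow-up means coincide and the level ANOVA rejects in 5%.
- If it starts 3 or 8 points lower, the follow-up means differ by 2 or 3 points and the level ANOVA rejects in 12% or 21%. In the 8-point case, the grade that improved most still has the worst score.
- For change, SD = 20 × √(2(1 − correlation)), which is 23.7, 20.0 and 15.5 at correlations 0.3, 0.5 and 0.7. ANOVA on change rejects in 39%, 52% and 75% with 166 per grade.

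**The case against.** **The text does not fix the dependent variable.** The sentence could describe when scores are taken, and Aim 1 and the responder rule both speak of improvement. This stands in part. It is an under-specified analysis whose natural reading is unsuitable, not a proven error.

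**Grade as a predictor of response already has an analysis.** A reader might infer that the plan has none. The documents do not support that: the regression is assigned the Aim 2 factors, which include grade and the baseline scores. What remains is narrower. Failure is undefined, and the only response definition nearby uses VAS. If failure is its converse, ASES and SST have no analysis of improvement by grade.

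**The pre-injection ANOVA is a safeguard.** This largely stands for big gaps: at 0/4/8 with 166 per grade, the unflagged chance is 5–7%, not 91%. It is weaker for moderate gaps. Seeing a gap also does not remove it from the follow-up test, and separate tests at each visit never test a difference in change.

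**Every number is assumed.** This is correct. Nothing in the protocol shows that grades differ at baseline, and the 5% masking figure needs exact cancellation.

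**Change is a choice of question.** This is also correct. With non-randomised grades, change and baseline-adjusted follow-up level answer different questions. In simulation with equal raw change, a baseline gradient of 0.4 SD (0.4 × 20 = 8 points) and about 500 patients, ANCOVA rejected in 24–67% at correlations 0.7 to 0.3. The plan should say which question it asks.

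**Conclusion.** The concern holds in a limited form. Read naturally, the post-injection grade ANOVAs compare levels and cannot tell a starting difference from a difference in response, while the study's title and Aim 1 are about response. That follows from Step 1 for any baseline difference between grades and needs no assumed number.

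The size does depend on assumptions. With SD 20, three equal grades and equal improvement, level ANOVAs reject in 16–91% over the gaps and group sizes tabulated. A reader might take the upper figures as the rate of misleading findings. The plan's own pre-injection test argues against that: the unflagged rate is about 5–21%, against about 5% for ANOVA on change. The defect is confined to this one comparison. It matters most for ASES and SST, which may have no other analysis of improvement by grade. It is worth correcting before analysis because the correction is cheap.

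**What to change.** - Run each post-injection grade comparison on change from baseline. Alternatively, fit one linear mixed model per score, with baseline and the five follow-ups as responses and with grade, time and grade-by-time terms, and judge grade on the grade-by-time contrast.
- Keep the pre-injection comparison as descriptive.
- Name the scale that defines grade.
- State that the target is the difference in change by grade, and that this is a different question from baseline-adjusted follow-up level because grades are not randomised.

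**Cost.** Revised analysis wording and slightly more analysis work. No new data are needed, because baseline and follow-up scores are already planned for every patient. There is a power cost if grades start equal and the baseline/follow-up correlation is below 0.5. At correlation 0.3, for a 5-point difference with 166 per grade, change has 39% power against 52% for levels. The two are equal at 0.5, and change is better above it.

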Subjects: Five hundred patients, both male and female, age 18-100 years, with a diagnosis of symptomatic primary osteoarthritis of the shoulder will be recruited from the patient population seeking treatment at the Orthopaedics Sports Medicine Institute. Subjects enrolled into the study will be those who have failed previous treatment including over-the-counter analgesics and activity modification, and have elected to receive a medically-indicated, ultrasound-guided IACSI in the shoulder. Two or three plain film views of the shoulder (including a Grashey and axillary lateral) obtained in accordance with standard of care prior to enrollment in the study will be reviewed. Once written informed consent has been obtained, subjects will complete the pre-procedural pain chart (Figure 1), ASES, VAS pain (at rest, with activity, at night), and SST scores. Upon completion of all outcomes measures, the ultrasound-guided IACSI (5cc of 1% lidocaine, 2cc of depomedrol (40mg/mL)) will be administered. Subjects will be asked to repeat the VAS pain score (at rest) 5-10 minutes following administration of the injection to assess the response to the anesthetic component of the injection. Upon conclusion of the visit, no clinical follow-up appointment will be scheduled, and subjects will be instructed to follow-up with their physician as needed; this is in accordance with standard of care for this patient population.

MRN: _____
 Date: _____
 Diagnosis: _____
 Injection: _____
 Pain: Pre: _____ post: _____
 Global: Yes No

Please shade in the areas where you are feeling pain now.
 Please mark with a dark circle (●) the areas where the pain is the worst.

(Figure 1: Pre-procedural pain chart, anatomic diagram)

Subjects will be contacted via email through the REDCap survey function or a phone call at two weeks, one month, two months, three months, and six months following the injection to complete the ASES, VAS pain (at rest, with activity, at night), and SST scores. If an email survey is not completed in REDCap, a reminder email will be sent every two days, up to two

times. If, after the final email reminder, the REDCap survey is still incomplete, a member of the study staff will call the subject and complete the survey via telephone call.

Exclusion Criteria: Patients will be excluded from the study for any of the following reasons:

- Post traumatic osteoarthritis
- Inflammatory osteoarthritis
- Imaging confirmed rotator cuff tear
- Prior ipsilateral shoulder surgery

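### Osteoarthritis grade is compared in up to 30 unadjusted one-way ANOVAs, none named as the one that counts, so the chance of a false grade result is well above 5%

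*Combined protocol and SAP*

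**What the plan says.** Section 6 (Research Plan), Data Analysis, sets the rule: "Each patient-reported outcome measure will be assessed at each time point pre- and post-injection and grouped according to the grade of shoulder osteoarthritis". The next sentence gives the test: "Groups will be compared using a one-way ANOVA analysis". A one-way ANOVA takes one outcome at one time, and no repeated-measures or multivariate test of grade is named.

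Section 6, Subjects, fixes the scores and times. Before injection, "subjects will complete the pre-procedural pain chart (Figure 1), ASES, VAS pain (at rest, with activity, at night), and SST scores". The same scores are collected again at "two weeks, one month, two months, three months, and six months following the injection". There is also one extra reading: "Subjects will be asked to repeat the VAS pain score (at rest) 5-10 minutes following administration of the injection".

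Section 5, Aim 1, counts the outcomes differently: "This will be determined through three patient-reported outcomes measures", namely ASES, VAS and SST.

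Data Analysis does not say which grading system it means. Aim 2 lists the "Samilson & Prieto Radiological Classification", with mild, moderate and severe categories, and separately the Walch classification.

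For these comparisons the document gives no significance level, multiplicity adjustment, primary outcome or visit, post-hoc rule or exploratory label. The only confidence level it states is for the pain-diagram proportions.

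**The concern.** Each ANOVA is another chance for grade to look important when it is not. Without a named comparison or an adjustment, any single score at any single visit with p below 0.05 could be reported as showing that grade affects response, and the plan has no rule for telling such a result from a real effect.

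This matters because radiographic grade is one of the predictors in Aim 2, and section 8 says the study may help providers predict response to injection. A chance signal at one visit could be taken as support for selecting patients by grade. The point is about the family of group tests, not about overfitting of the Aim 2 regression.

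**Working it through.** **No figure to reproduce.** The plan states no alpha, error rate or number of tests, so the count and the risk are both built up here.

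**Step 1: count the tests.** The scores are "ASES, VAS pain (at rest, with activity, at night), and SST scores", which is five with the three VAS items kept apart, or three on Aim 1's count. There are six time points: one before injection and five after.

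- Five scores: 5 × 6 = 30, of which 5 × 5 = 25 are post-injection.
- Three scores: 3 × 6 = 18, of which 3 × 5 = 15 are post-injection.
- The 5-10 minute VAS would bring 30 to 31.

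Pairwise tests between grades after a significant ANOVA would come on top.

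**Step 2: expected false positives.** At an assumed 0.05 per test with no effect of grade, the expected number is 0.05 × k whatever the correlation: 1.5 for 30 tests, 1.25 for 25, 0.9 for 18 and 0.75 for 15.

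**Step 3: chance of at least one if the tests were independent.** This is 1 − 0.95^k:

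- 1 − 0.95^30 = 0.785
- 1 − 0.95^25 = 0.723
- 1 − 0.95^18 = 0.603
- 1 − 0.95^15 = 0.537

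**Step 4: allow for correlation.** These are related scores repeated in the same patients, so independence gives an upper value. A null simulation used 500 patients (the planned number), three grade groups of 30/40/30%, no missing data, F-tests at 0.05 and 2,000 runs. The same correlation r was set between scores and between visits. The group split and the correlations are assumptions.

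| Tests | Independent (formula) | r = 0.4 | r = 0.6 | r = 0.8 | r = 0.9 |
|---|---|---|---|---|---|
| 30 | 79% | 67% | 54% | 32% | 21% |
| 25 | 72% | 62% | 49% | 30% | 20% |
| 18 | 60% | 54% | 41% | 27% | 18% |
| 15 | 54% | 47% | 37% | 25% | 17% |

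A separate simulation with three equal groups gave matching values where the settings coincide: for 30 tests, 33% at r = 0.8 and 22% at r = 0.9.

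**Step 5: check the remedy.** One test of grade per score over the five follow-ups, Holm-adjusted across five scores, gave a simulated familywise error of 3-5% at every correlation tried, provided the grades do not differ at baseline.

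If severe patients start worse and all grades improve equally, raw follow-up scores carry the old gap forward. With an assumed mild-to-severe gap of 0.2 SD, the Holm procedure on raw scores was significant 51% of the time at r = 0.6 and 34% at r = 0.8. Change from baseline gave 3-4%. The remedy therefore has to take baseline into account.

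**The case against.** The strongest reply has four parts.

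**The count.** A reader might infer that the plan runs exactly 30 tests. It never says so. Aim 1 counts three measures, which supports 18, and the pre-injection tests cannot show anything about response. This stands, so 30 is an upper count. It does not remove the problem: the lowest count, 15, still gives 17-47% over the same correlations.

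**The size.** A reader might infer that a false grade finding is likely, or quote 79%. That figure assumes independence. The risk passes one half only with the larger counts at low to moderate correlation. With 15 post-injection tests it stays below one half at every correlation of 0.4 or more, and at r = 0.8-0.9 it is about a third or less on every count. This also stands: the error is inflated, but the documents do not support calling a false finding likely.

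**The regression.** Data Analysis also specifies a regression for injection failure on the Aim Two factors, and the Samilson & Prieto grade is among them. So the plan does have one model aimed at grade and response, and it nowhere says that an isolated ANOVA p-value settles the matter. That is fair. But the regression is not labelled primary and its outcome visit is not named. Its presence does nothing to the error rate of the ANOVAs, which would still be reported with no rule for reading them.

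**The importance.** A reader might infer that grade is the gap this study was set up to fill. Section 4 says that the earlier study could not link grade to pain relief, which may simply be a null result. The gap it declares is the effectiveness of a single injection. Grade is one Aim 2 predictor among many.

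It could also be said that this is exploratory observational work. The document does not label these comparisons so.

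**Conclusion.** The concern holds in a limited form. As written, the grade comparison is a family of 15 to 30 unadjusted ANOVAs with none singled out. With no true effect, the chance of at least one false grade result is about 17-67%, at least three times the 5% of one named test.

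The range rests on an assumed 0.05 per test, correlations of 0.4 to 0.9, complete data on 500 patients and three grade groups. That the risk exceeds 5% holds on every count and correlation tried. Its exact size cannot be known from the documents. The issue affects how a grade finding may be read; it does not undermine the data collection. It should be settled before analysis, because a comparison chosen after seeing results does not restore error control.

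**What to change.** In Data Analysis, stop using the per-visit ANOVAs as the basis for any grade conclusion. Instead:

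- Name the Samilson & Prieto grade as the grouping.
- For each score, fit one repeated-measures model over the five follow-ups and test grade once, averaged over those visits. Analyse change from baseline, or adjust for the baseline score, and say which.
- Apply Holm across the scores. With five scores the smallest p-value is compared with 0.05/5 = 0.01; with three, 0.05/3 = 0.0167. State whether the three VAS items are tested separately.
- Show per-visit means by grade with confidence intervals and no significance claim.
- Treat the pre-injection comparison as a description of baseline only.

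The two baseline options are not equivalent here, because grade is not randomised. If all grades improve equally and the visit correlation is r, covariate adjustment still leaves (1 − r) of the baseline gap: 0.2 × (1 − 0.6) = 0.08 SD in the example above. Change from baseline leaves none, and it is the version that gave 3-4% in the check.

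The cost is a few sentences and slightly more analysis work, including a statement of how missed surveys are handled. No new data are needed. The downside is that a difference confined to one visit is harder to call significant.

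### One-way ANOVA at each survey uses only that survey's repliers, and neither the responder proportions nor the Aim 2 regression has a rule for missing data

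*Combined protocol and SAP*

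**What the plan says.** The cohort in section 6 (Research Plan, Subjects) is "Five hundred patients, both male and female, age 18-100 years". After the injection visit "no clinical follow-up appointment will be scheduled". Follow-up ASES, VAS pain and SST scores are collected by email survey or phone at "two weeks, one month, two months, three months, and six months following the injection". Non-response is chased: up to two email reminders go out, and then "a member of the study staff will call the subject and complete the survey via telephone call".

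The Data Analysis paragraph of the same section says "Each patient-reported outcome measure will be assessed at each time point pre- and post-injection", grouped by osteoarthritis grade, and then "Groups will be compared using a one-way ANOVA analysis". Response is defined as a VAS improvement above the minimal clinically important difference, which section 5 (Specific Aims) sets at more than 1.4 points. One multi-level regression is then fitted on the clinical and radiographic predictors of Aim 2, which section 5 lists under 12 headings (7 clinical, 5 radiographic).

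The plan does not state an expected non-response rate, a rule for a patient whose follow-up VAS is missing, or the time point at which response is judged. It also leaves out the levels of the multi-level model, any imputation and any sensitivity analysis.

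**The concern.** A one-way ANOVA has a single factor, here grade. Run at each time point, it can use only patients with a score at that time. It makes no adjustment for the baseline score and takes nothing from the same patient's other surveys. With outcomes collected remotely five times over six months, some surveys will probably go unanswered, and different patients may be absent each time. A change from one month to six months can then reflect a change in who replied as well as a change in pain or function.

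The responder proportions of Aim 1 are exposed in a different way. If patients who improved are more or less likely to reply than those who did not, the proportion among repliers is not the proportion in the cohort. For Aim 2, a regression with no stated handling of missing values may drop any patient lacking a predictor or the outcome, which costs precision.

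**Working it through.** The plan gives no figure to reproduce: the 500 has no stated power, responder rate or allowance for loss. From the documents come the enrolment of 500, the five surveys and the 12 predictor headings. Every missing rate below, and the true responder rate, is an assumption.

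**1. Who is in each ANOVA.** Let each survey be missed independently with probability m. Patients at one visit: 500 × (1 − m). Patients present at all five: 500 × (1 − m)^5. Patients with at least one survey: 500 × (1 − m^5).

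| m | One visit | All five | At least one |
|---|---|---|---|
| 10% | 450 | 295 | about 500 |
| 20% | 400 | 164 | about 500 |
| 30% | 350 | 84 | about 499 |

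At 20%, each ANOVA has 400 patients, but only 164 are common to all five. A longitudinal model could use nearly everyone. Independence overstates the turnover: if the same patients miss repeatedly, membership is steadier. Patients who never answer any survey contribute no follow-up score to either method.

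**2. Responder proportion among repliers.** With true rate p and reply rates a (responders) and b (non-responders), observed rate = pa / [pa + (1 − p)b].

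- Loss of 15% in responders and 30% in non-responders, p = 0.50: 0.425 / (0.425 + 0.350) = 0.425 / 0.775 = 54.8%, a bias of +4.8 points.
- Losses reversed: 0.350 / 0.775 = 45.2%, a bias of −4.8 points.
- Overall reply is 77.5%, so 500 × 0.775 = 387.5, about 388 patients. The 95% half-width there is 1.96 × √(0.25 / 387.5) = 5.0 points.
- Milder gap, 15% versus 25% loss: 0.425 / 0.800 = 53.1%, bias +3.1 points. Wider gap, 10% versus 30%: 0.450 / 0.800 = 56.3%, bias +6.3 points. Equal loss: no bias.

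**3. Bounds in the same scenarios.** Missing patients: 500 − 387.5 = 112.5.

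- Scenario giving 54.8%: observed responders 250 × 0.85 = 212.5. Missing as non-response: 212.5 / 500 = 42.5%. Missing as response: 325 / 500 = 65.0%.
- Scenario giving 45.2%: observed responders 250 × 0.70 = 175. The bounds are 175 / 500 = 35.0% and 287.5 / 500 = 57.5%.

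Each pair contains the true 50%. In the second scenario the lower bound alone (35.0%) is further from the truth than the unadjusted 45.2%, so one bound is not enough.

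**4. Aim 2 if incomplete records are dropped.** Patients kept = 500 × (outcome reply rate) × (1 − c)^k, with k predictors each missing independently at rate c.

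- k = 12, c = 2%, 20% of outcomes missing: 500 × 0.80 × 0.98^12 = 314.
- Same, with no outcome loss: 500 × 0.98^12 = 392.
- Items grouped into roughly six sources (pain chart, history, examination, questionnaires, films, post-injection VAS) that go missing together: 500 × 0.80 × 0.98^6 = 354.
- c = 1% and c = 5% with k = 12 and 20% outcome loss: 355 and 216.

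**The case against.** The strongest reply is that much of this is omission rather than a faulty method. It stands on several points.

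- **Complete-case analysis.** A reader might infer that the plan commits Aim 2 to a complete-case regression. The text does not say so. Multi-level may mean a mixed model that keeps patients with partial follow-up, or it may be loose wording for a multivariable regression. Even on the first reading, a record with a missing predictor would usually drop out unless imputation is specified, so the gap remains.
- **Loss of half the cohort.** A reader might infer that Aim 2 loses about half its patients. With 12 predictors that needs about 3.8% missing on each together with 20% outcome loss, or about 5.6% each with no outcome loss. The documents support no such rates. Baseline scores and the pain chart are completed before the injection, films predate enrolment, and the post-injection VAS is taken at the same visit, so predictor loss may well be small.
- **Effort against non-response.** The reminders and the staff call will reduce loss. They do not remove it, and no step follows an unanswered call.
- **Bias.** Nothing in the documents shows that replying depends on outcome, or in which direction.

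What the objection does not answer is the ANOVA. That method is named, and its dependence on each visit's repliers follows from the method itself.

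**Conclusion.** The concern holds for the grade comparisons as planned: one-way ANOVA at each time point uses a subset that can change between visits, without baseline adjustment or the patient's other surveys. A better method is available from the same data.

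For the responder proportions, bias is a risk and not a certainty. Under the assumed 50% true rate and 15% versus 30% losses it is 4.8 points in either direction. It is tempting to set this against the 4.4-point half-width at 500 patients (1.96 × √(0.25 / 500)) and call the bias larger than the sampling error. But that scenario leaves about 388 patients, where the half-width is 5.0 points, so the two are about equal.

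For Aim 2, some loss is possible because levels, time point and imputation are unstated. The illustration is about 314 of 500 kept, and more if items from one source go missing together. All these sizes rest on assumed missing rates.

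**What to change.** 1. Replace the per-visit ANOVAs with one repeated-measures mixed model per outcome over all five surveys, with time, grade, time-by-grade, baseline score and an unstructured covariance. Read the grade comparison at each time point from that model. It uses every survey returned.
2. Treat the responder proportions separately, because changing the ANOVA does not correct them. Name the time point at which response is judged, and use multiple imputation that includes the predictors and all other survey scores, earlier and later.
3. For Aim 2, state the outcome, the time point and what the levels are, and apply the same imputation to missing predictors and outcomes.
4. Report both bounds on each responder proportion: missing counted as non-response, and missing counted as response.

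The cost is revised analysis wording and modest programming, with no change to data collection. The mixed model and the imputation both rely on missing-at-random. The two bounds do not test that assumption; they show the range of proportions that the missing replies allow.
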